8.8.2 Device deficiencies

The parameters

- involved components
- safety and well-being of the patient affected
- consequences of the device deficiency

will be analysed using a frequency table.

Other details regarding the device deficiency will be listed only.

8.8.3 Medication

Coding of concomitant medication by ingredients will be conducted of *Implandata Ophthalmic Products*.

Concomitant medication during the Follow-up Phase (V09 until V13) will be shown as follows:

- Concomitant glaucoma medication of the study eye in total (N,%) and stratified by ingredients (N,%)
- Concomitant glaucoma medication other than study eye in total (N,%) and stratified by ingredients (N,%)
- Concomitant medication other indication than glaucoma in total (N,%) and stratified by ingredients (N,%)

The details regarding application forms, dosages, specified medications will be listed only.

9 Changes to Planned Analysis from Study Protocol

ARGOS-SC self-measurements were not recorded

Interim analyses are not performed according Note to File of 29.08.2022

10 References

1. ICH Topic E3: Structure and Content of Clinical Study Reports (CPMP/ICH/137/95 – July 1996).
2. ICH Topic E9: Statistical Principles for Clinical Trials (CPMP/ICH/363/96 – September 1998).
3. ARGOS-SC01_Follow-up (Clinical Investigation Plan), Rev. C, 27.05.2021.
4. Lawrence I-Kuei Lin (March 1989). "A concordance correlation coefficient to evaluate reproducibility". *Biometrics*. 45 (1): 255–268

11 Appendix

11.1 Concordance correlation coefficient

Concordance correlation coefficient (r_{ccc}) measures the agreement between two variables X and Y. Lawrence Lin has defined the form of the concordance correlation r_{ccc} as^[4]

$$r_{ccc} = 2 r s_x s_y / ((s_x^2 + s_y^2) + (m_x - m_y)^2)$$

with

$r = s_{xy}/(s_x s_y)$ (Pearson correlation coefficient)

m_x = mean of X

m_y = mean of Y

s_x = standard deviation of X

s_y = standard deviation of Y

s_{xy} = covariance of x and Y

The concordance correlation r_{ccc} has a range of -1 to 1. Values near +1 indicate strong concordance between x and y, values near -1 indicate strong discordance and values near zero indicate no concordance. There is no clear-cut agreement as to how to interpret the values, although one approach is to interpret Lin's r_{ccc} as for Pearson's correlation coefficient (e.g. values less than .20 are poor, while values greater than .80 are excellent).

11.2 Bland-Altman Plot

Bland and Altman introduced the Bland-Altman plot to describe agreement between two quantitative measurements by constructing limits of agreement. These statistical limits are calculated by using the mean and the standard deviation (s) of the differences between two measurements. To check the assumptions of normality of differences and other characteristics, they used a graphical approach.

The resulting graph is a scatter plot XY, in which the Y axis shows the difference between the two paired measurements (x-y) and the X axis represents the average of these measures $((x+y)/2)$. In other words, the difference of the two paired measurements is plotted against the mean of the two measurements. Bland-Altman recommended that 95% of the data points should lie within $\pm 2s$ of the mean difference. This is the most common way to plot the Bland-Altman method.

The bias is computed as the value determined by one method minus the value determined by the other method. If one method is sometimes higher, and sometimes the other method is higher, the average of the differences will be close to zero. If it is not close to zero, this indicates that the two assay methods are systematically producing different results.

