## 4.7.2 In vivo Studies

### 4.7.2.1 Animal Studies

#### Prove-of-concept study: "Tübingen I"

Six ARGOS-SC telemetric pressure transducers were implanted into the suprachoroidal space of 6 eyes from 6 New Zealand White rabbits. Functionality of each device was verified 1, 4, 8, 12 and 30 weeks after implantation on May 23 and May 24, 2014. After cannulation of the anterior chamber different intracameral pressure levels were generated using a height adjustable water column. Telemetric assessed IOP and intracameral pressure were analyzed using scatter plots and Bland-Altman analysis (95% CI). Mean bias (limits of agreement) 1, 4, 8, 12 and 30 weeks after implantation was 0.14 mmHg (-2.04 to 2.31 mmHg), 0.01 mmHg (-2.83 to 2.86 mmHg), 0.62 mmHg (-2.08 to 3.32 mmHg), 0.47 mmHg (-3.04 to 3.98 mmHg) and 0.33 mmHg (-2.75 to 3.42 mmHg) respectively. A slight variability of offset and proportional bias was explained with the mechanical stress that was exerted onto the implants due to the fact that the posterior chamber of the rabbit's eye differs significantly from the larger structures of the human eyes. In rabbit eyes the anterior segment is proportional larger and the posterior segment smaller than in human eyes [24], so mechanical stress and dislocation of the implant due to altered conditions is more likely in rabbit eyes.

Ophthalmological examinations showed no signs of conjunctival, scleral, choroidal or retinal lesions. Histological analyses revealed a small band of fibrosis next to the implantation site but showed no signs of inflammation, necrosis or other pathologies. Implantable telemetric suprachoroidal pressure sensors provided promising concordance between telemetric and intracameral IOP values. Clinical and histological examinations revealed good biocompatibility 30 weeks after implantation.

Devices used for this exploratory study were technology demonstrators which outer shape was not 100% identical with the final design. The purpose of this study was to prove the long term feasibility of suprachoroidal measurement of intraocular pressure. Technically, from a sensor and material point of view, devices were identical to the final devices. The devices were of rectangular shape (Dimensions: x mm x y mm x z mm), and encapsulated in PDMS silicone polymer with rounded edges.

Devices tended to slightly extrude out of the suprachoroidal cavity towards the incision, which was addressed in a follow-up study (see below).

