## 4.9 Clinical experience with similar devices

### 4.9.1 Method validation: Clinical experience with eyemate-IO

In the ARGOS-02 clinical trial, which involved the eyemate-IO device, surgical complications were reported in 7 of 23 patients. In five of those seven patients, complications occurred during the implantation of the eyemate-IO device. The complications most often (five times each) were Irisprolapse/floppy iris and pigment dispersion. Flat anterior chamber and “vis a tergo” (“pressure from behind”) were reported twice each.

Serious adverse events which were considered to be at least possibly related to either the implant or the implantation procedure were:

- Fibrin reaction in the anterior chamber (postoperative event which was resolved by medication)
- Increased intraocular pressure (was most likely caused by pigment dispersion)
- Corneal decompensation (was most likely caused by excessive surgical manipulation)

These complications are connected with the cataract surgical procedure and are possibly related to the implants position but not to the functional principle of the implant, and as such not associated with the ARGOS-SC device.

The eyemate-IO IOP measurement method showed an excellent level of concordance to the conventional GAT IOP measurement though a dependence of the differences between GAT IOP and eyemate-IO IOP on the respective IOP level was observed. In the range of physiological IOP ( $\leq 21$  mmHg), the differences between both methods are in the range of the physiological variety of IOP. In IOPs considered to be higher as normal ( $> 21$  mmHg) the differences between the two methods were higher than the average variety of IOP in human eyes. The higher the IOP the larger the difference between the methods, as also observed by other groups [28, 29].

IOP Implandata Ophthalmic Products GmbH	Clinical Investigation Plan ARGOS-SC01_Follow-up	Revision C
		Page 45 of 97

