8.5 Primary endpoint

8.5.1 Performance

Level of agreement between measurements made using GAT, Pascal DCT and ARGOS-SC system at visit V09 - V13.

The primary outcome measures of the study eye are:

- Average of 2 – 3 measurements using GAT system at visit V09 – V13
- Average of 2 – 3 measurements using ARGOS-SC system at visit V09 – V13 roughly contemporaneous with the GAT measurements

Descriptive statistics for the GAT and ARGOS-SC measures per visit.

Descriptive statistics for the absolute difference between ARGOS-SC and GAT measures per visit.

The absolute difference between the ARGOS-SC and GAT measures will be scaled in $\leq 5\text{mmHg}$ and $> 5\text{ mmHg}$ and the frequency distribution will be displayed.

The concordance of the intraindividual measurement values of GAT and ARGOS-SC will be indicated by the concordance correlation coefficient r_{ccc} (→ see section 11.1), separate for each visit.

The Bland-Altman (mean-difference) plot and a X-Y -plot (Scatter-Plot) should illustrate the comparison of the two methods (→ see section 11.2).

The level of agreement between Pascal DCT and ARGOS-SC will be evaluated analogously.

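### Limits of agreement are constant across IOP and no planned output estimates how the difference changes with IOP level, although the protocol reports such a change for the related eyemate-IO sensor

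*SAP*

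**What the plan says.** The primary objective (protocol 7.1.1, SAP 4.1.1) is to evaluate limits of agreement of ARGOS-SC with GAT and DCT. SAP 11.2 describes their construction: "These statistical limits are calculated by using the mean and the standard deviation (s) of the differences between two measurements". For checking the assumptions, the same section says only what the originators of the method did: "To check the assumptions of normality of differences and other characteristics, they used a graphical approach". It gives no rule for a plot that shows a trend.

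SAP 8.5.1 stratifies by visit only: "Descriptive statistics for the absolute difference between ARGOS-SC and GAT measures per visit". It adds a split at 5 mmHg, a concordance coefficient per visit, and Bland-Altman and scatter plots. DCT is handled in the same way. The mock-up of Table 2.1.1 has no slope and no row by IOP level. Figures 1 to 20 are one Bland-Altman plot and one scatter plot per visit and comparator. IOP level is not among the subgroup variables of protocol 9.7, and SAP 8.1.4 leaves the choice of subgroups to the data review meeting. Protocol 9.1.4 sets the criterion of 65% of pairs within 5 mmHg for more than 60 pairs, without regard to IOP level.

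On level dependence, protocol 4.9.1 praises the agreement of eyemate-IO with GAT, "though a dependence of the differences between GAT IOP and eyemate-IO IOP on the respective IOP level was observed", and continues: "The higher the IOP the larger the difference between the methods, as also observed by other groups". For ARGOS-SC in rabbits, protocol 4.7.2.1 says: "A slight variability of offset and proportional bias was explained with the mechanical stress that was exerted onto the implants".

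**The concern.** Limits from one mean and one SD describe agreement at a given IOP only if bias and spread are about the same at every IOP. The protocol's own background gives a reason to check this. According to protocol 4.9.1, eyemate-IO differences stayed within physiological variation up to 21 mmHg and exceeded the average variation of IOP above it. Protocol 4.7.1.4 says that ARGOS-SC rests on the same technology.

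The patients have had pressure-lowering surgery, so most paired readings are likely to be low, although the readable text gives no IOP distribution. An overall summary would then mainly describe low IOP. Protocol 3.3 calls peak values the ones thought most relevant to long-term outcome, and protocol 4.1 names detection of peaks as a purpose of the device. A favourable overall figure could be read as covering a range in which agreement was hardly tested or was poor.

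**Working it through.** **Inputs from the documents.** At most 24 patients (protocol 9.2), five visits V09 to V13, one GAT pair per visit: at most 24 pairs per plot and 24 × 5 = 120 in all. DCT pairs may be fewer, because DCT is used only where available. The criterion is 65% within 5 mmHg.

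**Inputs not in the documents.** Slope, bias and SD by IOP level, and the share of high readings. All are assumed below. The results show what is possible and predict nothing about this trial.

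**Formula.** With bias b and SD s, the share within 5 mmHg is Φ((5 − b)/s) − Φ((−5 − b)/s).

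**Illustration 1: bias rising with IOP.** Assume no bias at 14 mmHg, s = 2.5, b = slope × (IOP − 14), and 10% of pairs at 28 mmHg with the rest at 14.

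| Slope | Bias at 28 mmHg | Share at 14 | Share at 28 | Overall = 0.9 × low + 0.1 × high |
|---|---|---|---|---|
| 0.2 | 2.8 | 95.4% | 81.0% | 94.0% |
| 0.3 | 4.2 | 95.4% | 62.5% | 92.2% |
| 0.4 | 5.6 | 95.4% | 40.5% | 90.0% |

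**Illustration 2: bias and spread both larger at high IOP.** Assume low IOP b = 0, s = 3 (share 90.4%) and high IOP b = 8, s = 4 (share 22.6%). With a fraction h of pairs high, the pooled mean is 8h and the pooled variance is 9(1 − h) + 16h + 64h(1 − h).

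At h = 0.10 the mean is 0.8, the variance 8.1 + 1.6 + 5.76 = 15.46 and the SD 3.93. The pooled limits are 0.8 ± 1.96 × 3.93, or −6.9 to +8.5. The limits that would hold are ±5.9 at low IOP and +0.2 to +15.8 at high IOP. (SAP 11.2 uses 2s; this hardly matters here.)

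| Share of pairs high | 5% | 10% | 20% | 30% | 40% |
|---|---|---|---|---|---|
| Overall share within 5 mmHg | 87.1% | 83.7% | 76.9% | 70.1% | 63.3% |

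**When masking stops.** The overall share falls below 65% once h exceeds (low − 0.65)/(low − high). For 90% low and 20% high this is 0.25/0.70 = 35.7%. For low shares of 80 to 95% and high shares of 0 to 40% it ranges from 18.8% to 54.5%.

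**What the plots can show.** With 10% of pairs high there are 2.4 high points per plot and 12 over all visits. Assume an SD of pair means of 4 and a residual SD of 2.5. The 95% half-width of the slope is t × 2.5/(4 × √(n − 1)): 0.27 for n = 24 and 0.11 for n = 120 if pairs were independent. Repeated pairs from the same patient can change the second figure. A slope of 0.2 would therefore often be indistinguishable from zero at a single visit.

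**A caution on the slope.** It can be non-zero without any proportional bias. For error-prone readings X and Y of the same IOP it equals 2(Var X − Var Y)/(Var X + Var Y + 2 Cov). With assumed true-IOP SD 4, sensor error SD 1 and GAT error SD 2.5 this is 2(17 − 22.25)/(17 + 22.25 + 32) = −0.15.

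**The case against.** A reader might infer that the protocol shows ARGOS-SC to misread high IOP. It does not. Protocol 4.9.1 concerns eyemate-IO, which sits in the ciliary sulcus, and reports a difference from GAT. Protocol 8.2.2 says that DCT is believed closer to true IOP, especially at higher pressures, so GAT may be part of the source. The proportional bias in rabbits was slight and was attributed to rabbit anatomy. Over varied pressures, mean bias in that study was 0.01 to 0.62 mmHg, with all limits between −3.04 and +3.98. The porcine eye test gave an R² of 0.99 or better. The 224 human comparisons are in figures that could not be read here.

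A reader might also infer that every planned summary is invalid if bias varies with IOP. That goes too far. The share within 5 mmHg is a valid marginal proportion, and the concordance coefficient also needs no constant bias. Only reading the constant limits as applying at each IOP depends on the assumption.

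Nor is the plan blind. A Bland-Altman plot is the usual display for a level trend, and the SDs and Pearson correlation in Table 2.1.1 would let a reader work out each visit's slope on complete pairs. The study is exploratory, no tests are planned, and protocol 6.1 keeps ARGOS-SC values out of therapy decisions while they are not validated.

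All of this stands, and it limits the claim. It does not supply the missing estimate: a per-visit look at 24 points or fewer is unreliable, carries no rule, and leaves the combined information of five visits unused.

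**Conclusion.** The point holds as a gap in the agreement analysis and is a cheap improvement. The limits are constant across IOP within each visit, no output estimates level dependence, and the protocol gives a reason to look for it.

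The consequence is conditional on two things that the readable documents do not establish: that ARGOS-SC in human eyes shows the pattern reported for eyemate-IO, and that most readings are low. If both hold, constant limits misstate agreement at high IOP, and the 65% criterion can be met while agreement there is poor. Under the assumed inputs the overall share stays at 83.7 to 94.0% with 10% of pairs high, while the share at high IOP ranges from 22.6 to 81.0%. Masking ends once roughly 19 to 55% of pairs are high. The documents do not support a finding that the sensor is inaccurate at high IOP.

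**What to change.** Add to SAP 8.5.1, before database lock, an analysis that combines V09 to V13 with a patient random effect:

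1. The slope of the signed difference (ARGOS-SC minus GAT, and ARGOS-SC minus DCT) on the pair mean, with 95% CI, reported descriptively together with regression-based, level-dependent limits. State that unequal error variances alone can produce a non-zero slope, and that a slope against GAT is not by itself sensor error.
2. For pair means up to 21 mmHg and above 21 mmHg, the level at which protocol 4.9.1 divides the eyemate-IO results: number of pairs, number of patients, mean difference and share within 5 mmHg. Give limits in the upper row only if there are enough pairs.
3. A statement that the agreement conclusion covers the IOP range actually observed.

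The cost is SAP wording and one extra table, with no new data or visits. The row above 21 mmHg will probably be imprecise (about 12 of 120 pairs if 10% are high), and the picture may be less favourable than the overall figures.

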11.3 Statistical Analysis Package – Table of Contents

11.3.1 Tables

Table 1.1	Patient Disposition
Table 1.2	Baseline Characteristics
Table 2.1.1	IOP measures: GAT and ARGOS-SC
Table 2.1.2	IOP measures: DCT and ARGOS-SC
Table 2.2.1	User Acceptance Questionnaire for Investigator
Table 2.2.2	User Acceptance Questionnaire for Patient
Table 2.2.3	Standard deviation of IOP measures: GAT and ARGOS-SC
Table 2.3.1	Vision related Quality of Life Questionnaire
Table 2.3.2	Visual acuity (study eye)
Table 2.3.3	Visual acuity (fellow eye)
Table 2.3.4	Perimetry (study eye)
Table 2.3.5	Perimetry (fellow eye)
Table 2.3.6	Heidelberg Engineering ANTERION® (study eye)
Table 2.3.7	Heidelberg Engineering ANTERION® (fellow eye)
Table 2.3.8	Anterior segment (study eye)
Table 2.3.9	Anterior segment (fellow eye)
Table 2.3.10	Posterior segment (study eye)
Table 2.3.11	Posterior segment (fellow eye)
Table 3.1.1	Adverse Events
Table 3.1.2	Serious Adverse Events
Table 3.1.3	Device-related Adverse Events
Table 3.1.4	Device-related Serious Adverse Events
Table 3.2.1	Characteristics of Adverse Events
Table 3.2.2	Characteristics of Serious Adverse Events
Table 3.2.3	Characteristics of Device-related Adverse Events
Table 3.2.4	Characteristics of Device-related Serious Adverse Events
Table 3.3.1	Device Deficiencies
Table 4.1.1	Concomitant Medication of glaucoma
Table 4.1.2	Concomitant Medication of other indication

11.3.2 Figures

- Figure 1 ARGOS-SC vs. GAT at V09 (Bland-Altman Plot)
- Figure 2 ARGOS-SC vs. GAT at V09 (Scatter Plot)
- Figure 3 ARGOS-SC vs. GAT at V10 (Bland-Altman Plot)
- Figure 4 ARGOS-SC vs. GAT at V10 (Scatter Plot)
- Figure 5 ARGOS-SC vs. GAT at V11 (Bland-Altman Plot)
- Figure 6 ARGOS-SC vs. GAT at V11 (Scatter Plot)
- Figure 7 ARGOS-SC vs. GAT at V12 (Bland-Altman Plot)
- Figure 8 ARGOS-SC vs. GAT at V12 (Scatter Plot)
- Figure 9 ARGOS-SC vs. GAT at V13 (Bland-Altman Plot)
- Figure 10 ARGOS-SC vs. GAT at V13 (Scatter Plot)
- Figure 11 ARGOS-SC vs. DCT at V09 (Bland-Altman Plot)
- Figure 12 ARGOS-SC vs. DCT at V09 (Scatter Plot)
- Figure 13 ARGOS-SC vs. DCT at V10 (Bland-Altman Plot)
- Figure 14 ARGOS-SC vs. DCT at V10 (Scatter Plot)
- Figure 15 ARGOS-SC vs. DCT at V11 (Bland-Altman Plot)
- Figure 16 ARGOS-SC vs. DCT at V11 (Scatter Plot)
- Figure 17 ARGOS-SC vs. DCT at V12 (Bland-Altman Plot)
- Figure 18 ARGOS-SC vs. DCT at V12 (Scatter Plot)
- Figure 19 ARGOS-SC vs. DCT at V13 (Bland-Altman Plot)
- Figure 20 ARGOS-SC vs. DCT at V13 (Scatter Plot)

11.3.3 Listings

- Listing 1 Disposition of Subjects
- Listing 2 Visit Dates and Study Duration
- Listing 3 Ophthalmic Examination: Abnormal findings
- Listing 4 Concomitant Medication
- Listing 5 Device Deficiencies
- Listing 6 Adverse Events
- Listing 7 Serious Adverse Events

11.4 Statistical Analysis Package – Mock-up outputs (examples)

11.4.1 Tables

Table 1.2: Baseline characteristics

Table 1.2: Baseline characteristics		
Age [years]	N	n
	Minimum	xx.x
	Q1	xx.x
	Median	xx.x
	Q3	xx.x
	Maximum	xx.x
	Mean	xx.x
	Standard dev.	xx.x
	Mean [95% CI]	xx.x x.xx
Gender	N	n
	male	xx (xx.x%)
	female	xx (xx.x%)
Race	N	n
	Asian	xx (xx.x%)
	African	xx (xx.x%)
	Hispanic	xx (xx.x%)
	Caucasian	xx (xx.x%)
Please record the highest educational level the patient has completed	N	n
	Primary	xx (xx.x%)
	Intermediate	xx (xx.x%)
	A level	xx (xx.x%)
	University	xx (xx.x%)
	Vocational	xx (xx.x%)
	Other	xx (xx.x%)

Table 1.2: Baseline characteristics

	N	n
Duration of glaucoma [years]	Minimum	xx.x
	Q1	xx.x
	Median	xx.x
	Q3	xx.x
	Maximum	xx.x
	Mean	xx.x
	Standard dev.	xx.x
	Mean [95% CI]	xx.x x.xx
Type of glaucoma	N	n
	POAG	xx (xx.x%)
	NTG	xx (xx.x%)
	OHT/Glaucoma suspect	xx (xx.x%)
	PEX	xx (xx.x%)
	Other	xx (xx.x%)
Study eye	N	n
	left	xx (xx.x%)
	right	xx (xx.x%)

Table 2.1.1: IOP measures: GAT and ARGOS-SC

Table 2.1.1: IOP measures: GAT and ARGOS-SC						
		Visit V09	Visit V10	Visit V11	Visit V12	Visit V13
GAT [mmHg]	N	n	n	n	n	n
	Mean	x.xx	x.xx	x.xx	x.xx	x.xx
	SD	x.xx	x.xx	x.xx	x.xx	x.xx
	Q1	x.xx	x.xx	x.xx	x.xx	x.xx
	Median	x.xx	x.xx	x.xx	x.xx	x.xx
	Q3	x.xx	x.xx	x.xx	x.xx	x.xx
	Minimum	x.xx	x.xx	x.xx	x.xx	x.xx
	Maximum	x.xx	x.xx	x.xx	x.xx	x.xx
	95%-CI LL	x.xx	x.xx	x.xx	x.xx	x.xx
	95%-CI UL	x.xx	x.xx	x.xx	x.xx	x.xx
ARGOS-SC [mmHg]	N	n	n	n	n	n
	Mean	x.xx	x.xx	x.xx	x.xx	x.xx
	SD	x.xx	x.xx	x.xx	x.xx	x.xx
	Q1	x.xx	x.xx	x.xx	x.xx	x.xx
	Median	x.xx	x.xx	x.xx	x.xx	x.xx
	Q3	x.xx	x.xx	x.xx	x.xx	x.xx
	Minimum	x.xx	x.xx	x.xx	x.xx	x.xx
	Maximum	x.xx	x.xx	x.xx	x.xx	x.xx
	95%-CI LL	x.xx	x.xx	x.xx	x.xx	x.xx
	95%-CI UL	x.xx	x.xx	x.xx	x.xx	x.xx

Table 2.1.1: IOP measures: GAT and ARGOS-SC

		Visit V09	Visit V10	Visit V11	Visit V12	Visit V13
Difference ARGOS-SC - GAT [mmHg]	N	n	n	n	n	n
	Mean	x.xx	x.xx	x.xx	x.xx	x.xx
	SD	x.xx	x.xx	x.xx	x.xx	x.xx
	Q1	x.xx	x.xx	x.xx	x.xx	x.xx
	Median	x.xx	x.xx	x.xx	x.xx	x.xx
	Q3	x.xx	x.xx	x.xx	x.xx	x.xx
	Minimum	x.xx	x.xx	x.xx	x.xx	x.xx
	Maximum	x.xx	x.xx	x.xx	x.xx	x.xx
	95%-CI LL	x.xx	x.xx	x.xx	x.xx	x.xx
	95%-CI UL	x.xx	x.xx	x.xx	x.xx	x.xx
Difference	N	n	n	n	n	n
	≤ 5 mmHg	xx (xx.x%)				
	> 5 mmHg	xx (xx.x%)				
Pearson Correlation		x.XXX	x.XXX	x.XXX	x.XXX	x.XXX
r _{ccc}		x.XXX	x.XXX	x.XXX	x.XXX	x.XXX

Table 3.1.1: Adverse Events

Table 3.1.1: Adverse events				
SOC	PT	No. of AEs	No. of patients	%
Gastrointestinal disorders	Nausea	xx	xx	xx.x
	Diarrhoe	xx	xx	xx.x
	Total (SOC)	xx	xx	xx.x
Nervous system disorders		xx	xx	xx.x
		xx	xx	xx.x
	Total (SOC)	xx	xx	xx.x
	Total	xx	xx	xx.x

Table 3.2.1: Characteristics of Adverse Events

Table 3.2.1: Characteristics of Adverse Events

SOC / PT	N	No	Yes	SAE	Severity	Relationship with ...					Action taken					Outcome				
						Expected-ness	1	2	3	0	2	3	4	0	2	3	4	0	2	3
Gastrointestinal disorders	xx	xx	xx	xx	xx	xx	xx	xx	xx	xx	xx	xx	xx	xx	xx	xx	xx	xx	xx	xx
- Nausea	xx	xx	xx	xx	xx	xx	xx	xx	xx	xx	xx	xx	xx	xx	xx	xx	xx	xx	xx	xx
- Diarrhoe	xx	xx	xx	xx	xx	xx	xx	xx	xx	xx	xx	xx	xx	xx	xx	xx	xx	xx	xx	xx
Nervous system disorders	xx	xx	xx	xx	xx	xx	xx	xx	xx	xx	xx	xx	xx	xx	xx	xx	xx	xx	xx	xx
-	xx	xx	xx	xx	xx	xx	xx	xx	xx	xx	xx	xx	xx	xx	xx	xx	xx	xx	xx	xx
-	xx	xx	xx	xx	xx	xx	xx	xx	xx	xx	xx	xx	xx	xx	xx	xx	xx	xx	xx	xx
Total	xx	xx	xx	xx	xx	xx	xx	xx	xx	xx	xx	xx	xx	xx	xx	xx	xx	xx	xx	xx

Severity: 1=mild, 2=moderate, 3=severe

Relationship: 0=none, 2=possible, 3=probable, 4=causal relationship

Action taken: 1=ARGOS-SC Sensor removed, 2=subject withdrawn from study, 3=other

Outcome: 1=recovered, 2=recovered with sequelae, 3=recovering, 4=not recovered, 5=death

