#### 9.1.3 Safety Analysis

The incidence and nature of adverse events observed within the safety population will be analyzed by descriptive and explorative statistical methods.

Safety will be described in detail by frequency, seriousness, severity, nature and duration of events.

Number of adverse events as well as the number and relative frequency of patients reporting adverse events will be tabulated by system organ class and preferred terms. The same table will be prepared for serious adverse events. In addition, the number and relative frequency of patients reporting adverse events will be tabulated by system organ class and preferred terms in dependence on the worst severity and worst causal relationship. Furthermore, number of adverse device effects as well as the number and frequency of patients reporting adverse device effects will be tabulated by system organ class and preferred terms and not by event description as stated in the protocol.

 Implantata Ophthalmic Products GmbH	Clinical Investigation Plan ARGOS-SC01_Follow-up	Revision C  Page 70 of 97
--	---	---------------------------------

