### **10.3 Recording of Adverse Events (AEs)**

All AEs will be documented throughout the clinical trial as per ISO 14155, chap. 7.4.1, meaning from the point of inclusion/signing of the informed consent, until resolution or stabilization, or for a maximum of 7 days after the last subject has been discharged from the study.

All AEs will be reported on an Adverse Event Form, one for each Adverse Event, which is part of the CRF.

AEs will be collected with a non-leading question at each visit: "Have you had any new or worsening health problems since the last visit?" as well as by reporting those events directly observed and spontaneously reported by the subject. Clearly related signs, symptoms and abnormal diagnostic procedures should preferably be grouped together and recorded as a single diagnosis or syndrome whenever possible. Seriousness, severity (mild, moderate or severe), outcome and relationship to investigational device as well as expectedness and action taken will be recorded in the AE page of the CRF. Start and end date and time of the event will also be recorded. SAEs will be followed until resolution or stabilization. AEs will be followed until resolution or stabilization, or for a maximum of 7 days after the last subject has been discharged from the study.

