#### 10.3.4 Action taken

The investigator will document the action taken in relation to the investigational device and to other treatments. The categories in relation to the investigational device are:

- No action taken
- Device removed
- Subject withdrawn from the study
- Other, specify

IOP Implandata Ophthalmic Products GmbH	Clinical Investigation Plan ARGOS-SC01_Follow-up	Revision C
		Page 81 of 97

The categories in relation to other treatments are:

- No action
- Medication given (must be specified in the concomitant medication page)
- Non-medication treatment given (must be specified)
- Hospitalization
- Other, specify

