7.1 Derived variables

The table below provides the list of derived variables applicable for this study.

Variables	Formula
Demographic and baseline characteristics	
Age [years]	Year of baseline visit – year of birth
Derivation of duration	
Study duration [days]	Date of patient's last visit or date of study discontinuation (whatever the later date is) – date of baseline visit + 1

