8.8 Further safety analyses

8.8.1 Adverse events

All safety analyses will be conducted on the FAS set.

The AE terms will be coded according MedDRA into System Organ Class (SOC) and Preferred Terms (PT) of *Implandata Ophthalmic Products*.

Number of adverse events as well as the number and relative frequency of patients reporting adverse events will be tabulated by System Organ Class and Preferred terms.

The incidences of AEs will be stratified by:

- Seriousness
- Severity
- Relationship to medical device
- Expectedness
- Action taken
- Outcome
- Criterion to classify as serious

The incidence of AEs will be summarized to include only one occurrence of an AE class per patient. If a patient has multiple AEs of the same class, then that term will only be counted once. All AEs will be listed.

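### The protocol commits to describing adverse events by duration, but the SAP derives and tabulates no duration and does not declare the omission

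*SAP*

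**What the plan says.** Protocol 9.1.3 states: "Safety will be described in detail by frequency, seriousness, severity, nature and duration of events". Protocol 10.3 provides the data for this: "Start and end date and time of the event will also be recorded".

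SAP 7.1 opens with "The table below provides the list of derived variables applicable for this study" and then gives two variables, age and study duration. SAP 8.8.1 ("The incidences of AEs will be stratified by") names seven strata: seriousness, severity, relationship, expectedness, action taken, outcome and the criterion for seriousness. SAP 11.3.1 lists four tables of event characteristics, from 3.2.1 for all adverse events to 3.2.4, "Characteristics of Device-related Serious Adverse Events". None of the titles mentions duration. SAP section 9 declares two changes from the protocol: self-measurements were not recorded, and interim analyses are not performed.

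On action taken, Protocol 10.3.4 has two scales, one towards the device and one towards other treatments. The second includes "Medication given (must be specified in the concomitant medication page", "Non-medication treatment given (must be specified" and hospitalization. The legend of the example Table 3.2.1 in SAP 11.4.1 reads "Action taken: 1=ARGOS-SC Sensor removed, 2=subject withdrawn from study, 3=other".

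**The concern.** The study exists to assess the long-term safety of a permanent implant. How long an event lasted is part of that assessment, and some of the protocol's own events of interest depend on time: Protocol 7.3 defines hypotony partly by its persistence beyond one month and lists visual impairment as temporary. A count by preferred term, severity and outcome does not show how long a resolved event lasted. The protocol commits to this description, the dates are collected, and a reader of SAP section 9 would not learn that it had been left out.

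The treatment scale raises a similar but smaller question. Protocol 7.3 anticipates twelve kinds of follow-up procedure. The SAP's treatment tables (4.1.1 and 4.1.2) cover medication only and are not linked to events. If the action column shows only device or subject status, the tables do not show which events needed treatment.

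**Working it through.** The plan states no figure to reproduce here. The check sets the two documents side by side and counts.

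**1. Descriptors of safety.** Protocol 9.1.3 names five:

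| Descriptor | Where the SAP covers it |
|---|---|
| Frequency | 8.8.1, Tables 3.1.1–3.1.4 |
| Seriousness | 8.8.1 stratum, Tables 3.1.2 and 3.1.4 |
| Severity | 8.8.1 stratum, Table 3.2.1 shell |
| Nature | Organ class and preferred term, 8.8.1 |
| Duration | Not in 7.1, 8.8.1, the table titles of 11.3.1 or the AE shells of 11.4.1 |

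Four of five are covered. Section 9 declares two changes, and neither concerns duration. SAP 7.2 does have rules for completing partial start and stop dates when a period is calculated, so the derivation would need little more than a line in 7.1.

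**2. What the tables cannot show.** V09 is Day 365 (Protocol 8.3.15) and V13 is Day 1080 (Protocol Table 4). The span is 1080 − 365 = 715 days, or 715 / 30.44 ≈ 23.5 months. An event that starts and resolves within that span can last from one day to about 715 days. If its other attributes are equal, it takes the same place in Table 3.2.1 (outcome code 1, recovered) at either extreme.

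**3. What the tables do show.** The SAP outcome legend separates recovered, recovered with sequelae, recovering, not recovered and death. Unresolved events and events with sequelae are therefore distinguishable from recovered ones. Protocol 10.3.5 has four outcomes and uses a single ongoing category where the SAP has two (recovering, not recovered). The documents give no mapping between them.

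**4. Action categories.** The device scale in Protocol 10.3.4 has 4 categories (no action, removed, withdrawn, other). The treatment scale has 5 (no action, medication, non-medication treatment, hospitalization, other). Total: 4 + 5 = 9. The SAP legend has 3 codes, which match three of the four device categories. That leaves 9 − 3 = 6 without a code of their own: no action towards the device, and the whole treatment scale.

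**5. Onset.** Protocol 9.4 planned safety and performance summaries after V10, V11, V12 and V13, four in all. SAP 8.1.5 and section 9 say interim analyses are not performed. SAP 8.6.1 reports AEs over one period, V09 to V13, and that is also the period of the protocol's endpoint (8.1.3.2).

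**The case against.** The strongest reply is that little is lost. With at most 24 patients, every AE is listed individually (SAP 8.8.1, Listings 6 and 7). Duration is not part of the secondary safety endpoint, which names incidence, nature, severity and seriousness. The shells are headed as examples, the binding text in 8.8.1 says only action taken, and the header of Table 3.2.1 cannot be reconstructed from the extracted text. Hospitalization, and intervention to prevent permanent impairment, can appear through the seriousness criterion. Concomitant medication is tabulated by ingredient.

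Much of this stands, and it limits the point to the summary tables. It does not remove the point. Listings are not the description that 9.1.3 promises, and their columns cannot be confirmed, because the mock-up listing is not in the text available. The example legend is the only place in that text where the action codes are defined.

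A reader might be tempted by stronger conclusions, which the documents do not support:

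- *That persistent harm looks the same as brief harm.* The outcome codes separate unresolved events and sequelae from recovered events. Only the length of an event is lost.
- *That safety has no time axis.* SAP 8.7 analyses visual acuity, perimetry, slit-lamp, gonioscopy, OCT and fundus findings at V09 to V13, and abnormal findings are listed by patient and visit.
- *That pooling onset drops a protocol requirement.* The SAP follows the protocol's own endpoint period, and it declares that the interim analyses are not performed.
- *That a rising or falling event rate of some given size would be hidden.* The available text gives no event counts for months 12 to 36, so any such figure would be invented.
- *That the action column will be nearly empty.* The legend has a code for other, so this is conjecture.

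**Conclusion.** The point holds for duration. Following the SAP as written would leave an explicit protocol commitment unmet and undeclared: one of the five named descriptors is missing, and the AE tables contain no duration output. In those tables, recovered events lasting days and months cannot be told apart. The treatment-given point holds in a smaller form, since the one visible legend has no code for the protocol's treatment scale. Onset by interval is worth adding only as a descriptive extra, because the per-visit safety summaries were dropped and nothing restores a time pattern for AEs.

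This is a gap in descriptive reporting. It changes no primary result and no sample-size figure. The conclusion assumes that the visible table titles and shells represent the final tables. If the final tables or listings carry dates and treatment, the practical loss is smaller, but the missing summary still needs adding or declaring.

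**What to change.** 1. Add AE duration in days to SAP 7.1 and 8.8.1 and to Tables 3.2.1–3.2.4: median and range, with the number ongoing at last contact shown separately, and a rule for events already ongoing at V09. Otherwise, declare the omission and the reason in section 9.
2. Tabulate both action scales of Protocol 10.3.4, including no action, and state how the SAP's outcome codes map to the protocol's ongoing category. Confirm that Listings 6 and 7 carry start date, end date and treatment given.
3. Optionally, show AE onset by visit interval, with the number of patients under observation at the start of each interval.

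Protocol 10.3 and 10.3.4 already collect the fields, so the cost is SAP wording and a few columns. The downside is small cell counts with at most 24 patients, so the additions should be read descriptively only.
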